#### 4.1.5 Efficacy Scales

The following instruments that are used in this study are subject to statistical analysis:

##### 4.1.5.1 Alzheimer's Disease Assessment Scale - Cognitive Subscale 70 point (ADAS-cog):

- Range: The scale range is 0 to 70 with higher scores indicating greater cognitive impairment.
- Brief description: The ADAS-cog is a structured scale (approximately 40 minutes to complete) that evaluates memory, orientation, attention, reasoning, language and constructional praxis (Rosen, 1984). The ADAS-cog scoring range for the version used in this study is from 0 to 70. The ADAS-cog will be conducted at Baseline and at Months 3, 6, 9, 12, 15 and 18 or in the event of early termination. The ADAS-cog should always be administered prior to other cognitive measures.

##### 4.1.5.2 Mini Mental State Examination (MMSE):

- Range: The scale range is 0 to 30 with lower scores indicating greater cognitive impairment.
- Brief description: The MMSE is a brief 30-point test that is used to assess cognition (Folstein, 1975). It is commonly used to screen for dementia. In the time span of about 10 minutes, it samples various functions, including arithmetic, memory and orientation. The MMSE will be administered at Screening, Baseline, and at Months 3, 6, 12 and 18 or in the event of early termination. Participants with scores of 21-26 will be eligible for participation in the study.

##### 4.1.5.3 Controlled Oral Word Association Test (COWAT):

- Range: The score is the number of correct words. Lower numbers are associated with greater impairment.
- Brief description: The COWAT is a measure of verbal fluency in which the participant is asked to generate orally as many words as possible that begin with the letters "F", "A", and "S", excluding proper names and different forms of the same word (Borkowski, 1967, Loonstra 2001). For each letter, the participant is allowed one minute to generate the words. A comparable form of the test includes use of "C", "F" and "L," which may be used at alternate visits to reduce practice effect due to longitudinal testing on this task. Performance is measured by the total number of correct words produced summed across the three letters. Perseverations (i.e.,

repetitions of a correct word) and intrusions (i.e., words not beginning with the designated letter) are noted. Although fluency tests are sensitive to language dysfunction and deterioration of semantic knowledge, they can also reflect an inability to initiate systematic retrieval of information in semantic storage.

#### **4.1.5.4 Category Fluency Task (CFT):**

- Range: The score is the number of acceptable words produced. Lower numbers are associated with greater impairment.
- Brief description: The Category Fluency Test (CFT) is a measure of the subject's working memory and executive function. The CFT evaluates the spontaneous production of words beginning with a given letter, or of a given category, within 60 seconds. In this study, the participant is asked to orally produce as many animals as possible in one minute. Performance is measured by the number of acceptable words produced.

#### **4.1.5.5 Alzheimer's Disease Cooperative Study Activities of Daily Living Scale (ADCS-ADL):**

- Range: The scale range is 0-78, with lower scores indicating greater impairment.
- Brief description: The ADCS-ADL is an activity of daily living inventory developed by the ADCS to assess functional performance in participants with AD ([Galasko et al., 1997](#)). Informants are queried via a structured interview format as to whether participants attempted each item in the inventory during the preceding 4 weeks, as well as their level of performance. The ADCS-ADL will be administered at Baseline, and at Months 3, 6, 12 and 18 or in the event of early termination.

#### **4.1.5.6 Clinical Dementia Rating Scale (CDR):**

- Global CDR Range:
  - 0 = normal; healthy individuals
  - 0.5 = questionable dementia
  - 1 = mild dementia
  - 2 = moderate dementia
  - 3 = severe dementia.
- CDR sum-of-boxes (CDR-sb) range: CDR-sb scores range from 0 to 18 with higher scores indicating greater cognitive impairment.
- Brief description: The CDR scale is used as a global measure of dementia and is completed by a clinician in the setting of detailed knowledge of the individual patient collected from interviews with the patient and caregiver ([Berg, 1988](#)). The CDR describes 5 degrees of impairment in performance on each of 6 categories including memory, orientation, judgment and problem solving, community affairs, home and hobbies, and personal care. Much of the information will therefore already have been

gathered, either as part of normal clinical practice or as part of a research study. The interview takes approximately 40 minutes to administer.

The scores for each category can also be summed and this is known as the sum of box score (CSR-SB). The CDR will be conducted at Baseline and at Months 3, 6, 12 and 18 or in the event of early termination. To avoid patient fatigue, the CDR should be performed on a separate visit day than the other cognitive tests.

#### **4.1.5.7 Neuropsychiatric Inventory (NPI):**

- Range: Scores range from 0-144 with higher scores indicating a greater presence of neuropsychiatric symptoms.
- Brief description: The NPI is a well-validated, reliable, multi-item instrument to assess psychopathology in AD based on an interview with the caregiver ([Cummings et al, 1994](#), [Cummings, 1997](#)). The interview is also relatively brief (15 minutes). It evaluates both the frequency and severity of 12 behavioral areas including delusions, hallucinations, dysphoria (depression) anxiety, agitation/aggression, euphoria, disinhibition, irritability, lability, apathy, aberrant motor behavior, appetite and eating changes and night-time behaviors.

Frequency assessments range from 1 (occasionally, less than once per week) to 4 (very frequently, once or more per day or continuously) as well as severity (1= mild, 2 = moderate, 3 = severe).

Distress is rated by the study partner or caregiver and ranges from 0 (no distress) to 5 (very severe or extreme). Distress is captured separately from the total score.

The overall score and the score for each subscale are the product of severity and frequency. The NPI will be administered at Screening, Baseline, and at Months 3, 6, 12 and 18 or in the event of early termination.

#### **4.1.5.8 Resource Utilization in Dementia (RUD):**

- Resource questionnaire with limited statistical evaluation as an instrument.
- Brief description: The RUD is a validated and reliable questionnaire which assesses the health care resource utilization (HCRU) of the patient and caregiver and measures the level of formal and informal care ([Wimo et al, 2012](#)). The RUD consists of items about caregiver time, caregiver work status, caregiver HCRU (e.g., hospitalization, ER visits, health care professional visits and medication), patient living accommodation, and patient HCRU. It takes approximately 15-20 minutes to complete and is usually interview administered by any health care professional. This scale will be administered at Baseline and at Months 6, 12 and 18 or in the event of early termination.

#### 4.1.5.9 Dementia Quality of Life (DEMQOL) – Proxy:

- Range: The scale range is 31—124, with lower scores indicate greater impairment.
- Brief description: The DEMQOL-Proxy questionnaire is a validated and reliable questionnaire that is interview administered and completed by the caregiver about the patient’s health related quality of life ([Smith et al, 2005](#)). It consists of 31 items representing 5 domains (daily activities and looking after oneself, health and well-being, cognitive functioning, social relationships, and self-concept) and takes approximately 20 minutes to complete. Higher scores indicate better health-related quality of life. This scale will be administered at Baseline and at Months 6, 12 and 18 or in the event of early termination. Item 32 is a global quality of life question that elicits an overall assessment of the patient’s general quality of life.

#### 4.1.5.10 Trail-making Tests (TMT) “A” and “B”:

- Range: 150 seconds maximum for “A” and 300 seconds maximum for “B.”
- Brief description: The Trail-making tests “A” and “B” score is the number of seconds needed to complete the trails with maximum values specified ([Reitan, 1958](#)). Part A consists of 25 circles numbered 1 through 25 semi-randomly distributed over a white sheet of 8 1/2" X 11" paper. The participant is instructed to connect the circles with a pencil line as quickly as possible in ascending numerical order. Part B also consists of 25 circles, but these circles are either numbered (1 through 13) or contain letters (A through L). Now the participant must connect the circles while alternating between numbers and letters in an ascending order (e.g., A to 1; 1 to B; B to 2; 2 to C). Lower scores (seconds) indicate greater cognitive function.

## 4.2 Safety Variables

Safety is monitored in this study by collection of adverse events, vital signs, electrocardiography, and clinical laboratory measures. It is noted that all untoward events or experiences are reported as adverse events regardless of whether they are identified by clinical observation, subject reporting, physical examination, clinical laboratory test result, electrocardiography, or any other examination or test. It is noted that listings of vital signs, laboratory data, electrocardiograms (ECG), and all safety data from all other sources are reviewed by medically qualified individuals to ensure that safety signals are identified and reported in the analysis of the safety data from this study.

### 4.2.1 Treatment-emergent Adverse Events

Adverse events will be coded using Medical Dictionary for Regulatory Activities (MedDRA) Version 16.0 or above. Adverse event coding will be done to the lowest level term (LLT). Adverse events will be summarized by System Organ Class (SOC) and preferred terms (PT).

Definitions:

- A treatment-emergent adverse event (TEAE) is an event that is observed or reported after administration of study medication that was not present prior to study medication administration or an event that represents the exacerbation of a pre-existing event.
- An adverse withdrawal is a subject who withdrew from the study due to an adverse event.
- A serious adverse event (SAE) is an AE that is classified as serious according to the criteria specified in the study protocol.

Safety and tolerability variables based on adverse events include the following:

- Proportions of subjects with TEAEs by Preferred Term and decreasing frequency of AEs
- Proportions of subjects with TEAEs by System Organ Class and Preferred Term
- Proportions of subjects with related TEAEs
- Proportions of subjects with severe TEAEs
- Proportions of subjects who died.
- Proportions of subjects with treatment-emergent SAEs other than death.
- Subjects with TEAEs that result in study termination.

#### 4.2.2 The Columbia Suicide Severity Rating Scale (C-SSRS)

- Range: The following outcomes are C-SSRS categories and have binary responses (yes/no). The categories have been re-ordered from the actual scale to facilitate the definitions of the composite and comparative endpoints, and to enable clarity in the presentation of the results.
  - Category 1 – Wish to be Dead
  - Category 2 – Non-specific Active Suicidal Thoughts
  - Category 3 – Active Suicidal Ideation with Any Methods (Not Plan) without Intent to Act
  - Category 4 – Active Suicidal Ideation with Some Intent to Act, without Specific Plan
  - Category 5 – Active Suicidal Ideation with Specific Plan and Intent
  - Category 6 – Preparatory Acts or Behavior
  - Category 7 – Aborted Attempt
  - Category 8 – Interrupted Attempt
  - Category 9 – Actual Attempt (non-fatal)
  - Category 10 – Completed Suicide

Self-injurious behavior without suicidal intent is also a C-SSRS outcome (although not suicide-related) and has a binary response (yes/no).

The following outcome is a numerical score derived from the C-SSRS categories. The score is created at each assessment for each patient and is used for determining treatment emergence.

**Suicidal Ideation Score:** The maximum suicidal ideation category (1-5 on the C-SSRS) present at the assessment. Assign a score of 0 if no ideation is present.

- Brief description: The Columbia Suicide Severity Rating Scale (C-SSRS) is a joint interview with the caregiver and patient that systemically assesses suicidal ideation and suicidal behavior (Posner et al, 2007). This scale will be administered at Screening Visit to evaluate life time suicide attempt, suicide behaviors, and other non-suicidal self-injuries. Positive responses on the C-SSRS will be mapped to the Columbia Classification Algorithm of Suicide Assessment (C-CASA) for classification and reporting using a standard algorithm.)

#### 4.2.3 Vital Signs

Vital signs measurements consist of blood pressure and pulse rate. Variables of analysis will include means, mean changes over time, and proportions of subjects meeting criteria for potential clinical concern in vital signs:

- Mean and mean changes in systolic and diastolic blood pressures
- Mean and mean changes in pulse
- Proportions of subjects with treatment-emergent values or changes of potential clinical concern.

#### 4.2.4 Clinical laboratory assessments

Routine clinical laboratory data will be summarized with descriptive statistics on assessment values and change from Baseline. Routine clinical laboratory data will also be evaluated on the basis of laboratory-defined reference ranges and criteria defining potential clinical concern for values or changes, as defined in this document ([Section 10](#)). Routinely collected laboratory safety data that are not required by the protocol will be considered source data, and will not be captured for inclusion into the study database.

Definition:

- A treatment-emergent abnormal value (TEAV) is a laboratory value that is abnormal after administration of study medication that was normal prior to study medication administration.
- A TEAV of potential clinical concern is a value or change that meets criteria specified in this SAP in Section 10.

Laboratory analytes in this study include:

- Hematology
  - Hemoglobin
  - Hematocrit
  - Erythrocyte (RBC) count
  - Platelet count
  - Total leukocyte (WBC) count

- MCV
- Leukocyte differential (percent and total)
  - Total neutrophils
  - Eosinophils
  - Monocytes
  - Basophils
  - Lymphocytes
- Clinical chemistry
  - BUN
  - Creatinine
  - Glucose
  - HbA1c
  - Calcium
  - Sodium
  - Potassium
  - Chloride
  - Bicarbonate
  - AST
  - ALT
  - GGT
  - LDH
  - Total bilirubin
  - Alkaline phosphatase
  - Uric acid
  - Albumin
  - Total protein
  - Phosphorus

Safety variables of analysis include:

- Subjects with TEAVs
- Subjects with TEAVs of potential clinical concern (based on criteria in this SAP)
- Subjects with a TEAV in a liver enzyme function test (LFT).

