5. Specific exclusionary brain MRI findings (as identified on the central MRI read) as determined by the investigator that could either significantly contribute to the patient's current cognitive or functional decline, impair his/her ability to fully participate in the trial or that may impact his/her status during 18-month course of the trial. In any case, 10 or more microhemorrhages as identified by the central reading, is exclusionary. Grade three deep white matter changes (diffuse involvement of entire region) on the central reading report is exclusionary. If a head CT is used for assessment of eligibility, structural abnormalities as determined by the investigator that could either significantly contribute to the patient's current cognitive or functional decline, impair his/her ability to fully participate in the trial or that may impact his/her status during 18-month course of the trial would be exclusionary.
6. A current primary diagnosis of major psychiatric disorder, e.g., schizophrenia, bipolar disorder, major depressive disorder, or other severe psychiatric illness per the DSM-IV-TR criteria per the investigator's judgment.
7. Serious suicide risk per the following criteria:
 - Suicidal ideation associated with intent and/or plan within the previous year as indicated by a "yes" answer on Items 4 or 5 of the C-SSRS or,
 - History of suicidal behavior within the previous 10 years as indicated by a "yes" answer to any of the suicidal behavior items of the C-SSRS with a behavior occurring within the previous 10 years or,
 - Lifetime history of serious or recurrent suicidal behavior.
8. History of cancer within the last 5 years except adequately treated cervical carcinoma in-situ, cutaneous basal cell or squamous cell cancer, or non-progressive prostate cancer not requiring treatment.
9. Current (e.g., within the last 3 months) body mass index (BMI) of greater than or equal to 35 kg/m² or a current (e.g., within the last 3 months) weight less than 45 kg.
10. Any clinically significant hepatic or renal disease, elevated transaminase levels of greater than 1.5 times the upper limit of normal (ULN), creatinine greater than 1.5 x ULN.

11. Patients with unstable, uncontrolled diabetes ($HbA1c > 7.7\%$) and those requiring insulin.

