8.0 ADVERSE EVENT REPORTING

8.1 ADVERSE EVENTS

An adverse event (AE) is any untoward medical occurrence in a clinical study participant administered a pharmaceutical product. Study drug treatment does not necessarily have a causal relationship with the AE. An AE, therefore, can be any unfavorable change in structure, function or chemistry (including abnormal clinical lab results, or ECG findings), symptoms, signs, or diseases temporally associated with the use of a medicinal (investigational) product, whether or not related to the medicinal (investigational) product, as defined by ICH.

The criteria for determining whether an abnormal objective test finding should be reported as an adverse event are as follows:

- Test result is associated with accompanying symptoms, and/or
- Test result requires additional diagnostic testing or medical/surgical intervention, and/or
- Test result leads to a change in study dosing or discontinuation from the study, significant additional concomitant drug treatment, or other therapy, and/or
- Test result is considered to be an adverse event by the investigator or sponsor.

Repeating an abnormal test, in the absence of any of the above conditions, does not constitute an adverse event. Any abnormal test result that is determined to be an error does not require reporting as an adverse event.

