#### **5.4.3 Routine Clinical Laboratory Measurements**

Because “exacerbations” of pre-existing abnormalities in laboratory analytes are examined using clinical judgment and are reported as TEAEs, additional analysis on TEAEs is limited to subjects with values that are normal prior to dosing and abnormal after dosing. Potentially clinically significant abnormalities in laboratory analytes are to be reported as TEAEs and summarized as clinical TEAEs.

Subjects with clinical laboratory data meeting the criteria in [Section 10](#) of this SAP for values of potential clinical concern will be flagged and summarized. Proportions of subjects with clinical laboratory values of potential clinical concern will be examined for the treatment groups.

For each post-Baseline assessment, descriptive statistics are provided for the assessment value and the change from Baseline to the assessment with mean, median, standard deviation, minimum, and maximum at each assessment time.

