## 10 Values of Potential Clinical Concern

Parameter	Threshold (study-specific threshold calculated)
Hematology	
Hemoglobin	<8.5 g/dL
Hematocrit	<25 %
WBC (Leukocytes)	<0.6 x LLN (<2.1 10  /uL)
Platelets	<0.5 x LLN (<70 10  /uL)
Total Neutrophils (Abs)	<0.8 x LLN (<0.8 10  /uL)
Lymphocytes (Abs)	<0.6 x LLN (<0.6 10  /uL)
Chemistry	
Total bilirubin	>2.5 x ULN (>2.7 mg/dL)
AST	>3 x ULN (>102 U/L)
ALT	>3 x ULN (>123 U/L)
Alk Phosphatase	>3 x ULN (>348 U/L)
Creatinine	>2 mg/dL
BUN	>1.4 x ULN (30.8 mg/dL)
Glucose	≤70 mg/dL or ≥270 mg/dL
Uric acid	>12 mg/dL
Sodium	<125 mmol/L or >155mmol/L
Potassium	<3.0 mmol/L or >6.0 mmol/L
Bicarbonate	<16 mmol/L
Calcium	<6.0 mg/dL and >13.0 mg/dL
Triglycerides	>750 mg/dL
Electrocardiogram	
Heart Rate	<50 bpm and ≥/=25% decrease from baseline >100 bpm and ≥/=25% increase from baseline
PR interval	≥200 msec and ≥25% increase from baseline
QRS interval	≥200 msec and ≥25% increase from baseline
QTc interval	≥500 msec ≥30-60 msec increase >60 msec increase
Vitals (sitting)	
SBP	≥190 mmHg (entry is <180 mmHg) Systolic <80 mm Hg Decrease from baseline ≥30 mmHg
DBP	≥120 mmHg (entry is <105) <50 mm Hg

Parameters not provided with specific thresholds for clinical concern: RBC count, eosinophils, basophils, monocytes, direct or indirect bilirubin (just total as shown above), chloride, albumin, total protein, insulin, total cholesterol, HDL, LDL, urinalysis, pulse rate from VS (rely on ECG heart rate).

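### SAP 4.2.4 and 5.4.3 give no systematic count of laboratory worsening in patients whose value is already abnormal at entry

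*SAP*

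**What the plan says.** SAP 4.2.4 counts a laboratory value as treatment-emergent when it is "abnormal after administration of study medication that was normal prior to study medication administration". Protocol 9.6.1.3 defines TEAVs in the same way, as shifts from normal to abnormal.

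SAP 5.4.3 gives the reason. Exacerbations "of pre-existing abnormalities in laboratory analytes are examined using clinical judgment and are reported as TEAEs", so the further analysis "is limited to subjects with values that are normal prior to dosing and abnormal after dosing". (That sentence says TEAEs where TEAVs is probably meant.) The TEAE definition in SAP 4.2.1 does include "an event that represents the exacerbation of a pre-existing event".

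SAP 5.4.3 also flags subjects whose laboratory data meet a Section 10 limit, and SAP 5.4.4 summarizes subjects with AST or ALT of at least 3 x ULN together with bilirubin of at least 2 x ULN. Neither states a condition on the baseline value. Section 10 closes with a list that begins "Parameters not provided with specific thresholds for clinical concern: RBC count, eosinophils, basophils, monocytes". Values and changes from baseline are summarized descriptively at each assessment.

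**The concern.** A patient who is abnormal before dosing cannot have a TEAV in the same analyte, however far the value moves. The SAP relies on adverse-event reporting to pick up such patients, but that reporting is conditional. Under protocol 8.1 an abnormal test becomes an adverse event if it meets at least one of four criteria. The first is "Test result is associated with accompanying symptoms, and/or"; the others are further work-up or intervention, a change in dosing or added treatment, and the view of the investigator or sponsor. A silent numerical rise need not meet any of them.

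What is at stake is how complete the categorical safety tables are. Patients who enter with a raised value are a natural group in which to look for further worsening, and the plan has no table that counts it by rule. The TEAV denominator is also unstated. If it is all treated subjects, the percentage includes people who could not have the event.

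**Working it through.** No figure in the plan can be reproduced here, because the point concerns definitions. The check sets the sections side by side.

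**1. Can patients enter abnormal?** Yes. Protocol 4.2 (criterion 10) excludes transaminases only above 1.5 x ULN, so values between 1.0 and 1.5 x ULN are admitted. Protocol 4.1 (criterion 12) admits other out-of-range results that the investigator judges not clinically significant.

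**2. Which routes could count worsening from an abnormal baseline?**
- TEAV (SAP 4.2.4, 5.4.3): no, by definition.
- Section 10 flag: yes, if the absolute limit is crossed. The laboratory rows contain no change criterion, although SAP 4.2.4 speaks of values or changes.
- SAP 5.4.4: yes, if both liver criteria are met.
- Adverse event: yes, if reported under protocol 8.1.

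One ambiguity remains. SAP 4.2.4 calls a Section 10 case a TEAV of potential clinical concern, which suggests a normal baseline, while its wording and the flag in 5.4.3 state none.

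**3. How many analytes have a Section 10 limit?** SAP 4.2.4 lists 11 hematology and 19 chemistry analytes: 11 + 19 = 30. Section 10 has 6 hematology and 13 chemistry rows. One of these, triglycerides, is not in the 4.2.4 list, so 6 + 12 = 18 analytes have a limit and 30 - 18 = 12 do not.
- Seven are openly listed as having none: RBC, eosinophils, basophils, monocytes, chloride, albumin, total protein.
- Five are not mentioned in Section 10: HbA1c, GGT, LDH, MCV, phosphorus.

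Protocol Appendix 1 has a GGT row (above 3.0 x ULN) and none for the other four. SAP Section 10 omits GGT without comment, and SAP 1.9 declares only the removal of Bazett's correction. Protocol 9.0 says that the SAP supersedes.

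**4. An example.** Section 10 gives the ALT limit as 3 x ULN = 123 U/L, so ULN = 123 / 3 = 41 U/L. Take a rise from 1.4 to 2.9 x ULN:
- Entry: 1.4 x 41 = 57.4 U/L, below the exclusion level of 1.5 x 41 = 61.5 U/L, so the patient is admitted.
- Later: 2.9 x 41 = 118.9 U/L, below 123 U/L.

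The value has roughly doubled (2.9 / 1.4 = 2.07). It is not a TEAV, a Section 10 flag or a 5.4.4 case. It is counted only if someone reports it as an adverse event.

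**5. Possible size.** The documents give no baseline abnormality rates. Let q be the fraction abnormal at entry for an analyte, assumed to be 10-30%, with about 400 patients per arm.
- Patients per arm who cannot have a TEAV: 400 x 0.10 = 40 to 400 x 0.30 = 120.
- With all subjects as denominator, reported rate = at-risk rate x (1 - q). An illustrative at-risk rate of 10% would be shown as 10% x 0.90 = 9% to 10% x 0.70 = 7%.

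**The case against.** The best defence is that the restriction is deliberate, follows the protocol's own definition, and sits within a descriptive safety analysis with several other safeguards. Much of that stands, and it rules out some stronger readings.

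- A reader might infer that worsening in abnormal entrants is never counted. The documents do not support this: the Section 10 and liver-injury counts state no normal-baseline condition, and exacerbations can be TEAEs.
- A reader might infer that such patients are shut out of liver safety. They are not. Protocol 7.1.5.2(b) has a rule for patients whose AST or ALT is raised at baseline, and potential liver-injury cases are reported as serious adverse events. It does not reach the example above, since it also needs at least 3 x ULN and raised bilirubin.
- A reader might infer that an effect in these patients would show only as a diluted mean. SAP 5.4.3 also gives the median, standard deviation, minimum and maximum of value and change at each assessment. Protocol 9.6.2 plans summaries of change to each subject's minimum and maximum, and SAP 6.6 refers to minimum and maximum over time.
- A reader might single out HbA1c, GGT and LDH. They are three of 12 analytes without a Section 10 limit, and glucose and the main liver tests do have limits.

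SAP 4.2 adds that medically qualified staff review laboratory listings, and the last criterion in protocol 8.1 is open-ended. Randomization should also make any dilution similar in the two arms, so no between-arm bias follows.

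None of this supplies a rule-based count of patients who worsened from an abnormal baseline. Listing review and adverse-event reporting rest on judgement, and distribution summaries do not give the number of patients affected.

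**Conclusion.** The point holds in a narrow form. The TEAV count omits patients who enter abnormal, and no other table counts their worsening systematically. It is counted only through an absolute Section 10 limit, the SAP 5.4.4 criteria or judgement-based adverse-event reporting. For 12 of 30 analytes only the last of these gives a count, although descriptive change and minimum/maximum summaries remain.

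The size cannot be determined from the documents. The 40-120 patients per arm rest on the assumed 10-30% rate, and the dilution also assumes an all-subjects denominator, which the SAP does not state. Efficacy inference and alpha are untouched. This is a cheap improvement to safety reporting and does not invalidate the safety analysis.

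**What to change.** In SAP 4.2.4 and 5.4.3:

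1. Add shift tables of baseline category (low, normal, high) by worst post-baseline category for every analyte. Include a descriptive count of worsening from an abnormal baseline; for liver tests, tabulate the highest post-baseline multiple of ULN against the baseline multiple.
2. Define the TEAV denominator as patients normal at baseline for that analyte.
3. State that the Section 10 count applies whatever the baseline status.
4. Reconcile the GGT criterion between protocol Appendix 1 and SAP Section 10.

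All of this uses data already collected and needs no new procedure. The cost is SAP wording, some programming and a few more safety tables to review.
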